Table 8-6 Mandatory dose modification requirements and recommended clinical management guidelines for "other" potential immune-related AEs of special interest

Grade	Recommended Adverse Event management guidelines	Mandatory Dose Modification requirements					
Mild (Grade 1)	Provide symptomatic treatment	Continue spartalizumab					
Moderate (Grade 2)	 Consider interruption of spartalizumab until recovery to ≤ Grade 1 or baseline. 						
	Ensure adequate evaluation to confirm etiology or exclude other causes						
	Provide symptomatic treatment						
	Systemic corticosteroids may be indicated						
	Consider biopsy for confirmation of diagnosis						
	A specialist should be consulted						
Severe (Grade 3)	 Initiate systemic corticosteroids (prednisone or equivalent) at a dose of 1-2 mg/kg QD and other therapies as appropriate Monitor closely and consult with a specialist 	 1st occurrence: Interrupt spartalizumab until recovery to ≤ Grade 1 or baseline May restart spartalizumab treatment at the same dos and schedule 					
		AE resolution to ≤ Grade 1 or baseline must occur within a maximum period of 12 weeks sind					

Protocol/Version No.: 5, Date December 15, 2022

Other(e.g. Autoimmune neuropathy, Demyelinating polyneuropathy, Guillain Barre, Myasthenia Gravis-like syndrome, Non-infectious myocarditis, pericarditis, pancreatitis, encephalitis, and Grade 3 Fatigue with rapid onset in absence of disease progression)

Grade	Recommended Adverse Event management guidelines	Mandatory Dose Modification requirements
		a Grade 3 event has been identified, otherwise spartalizumab must be permanently discontinued.
		2 nd occurrence: Permanently discontinue spartalizumab
Grade 4	Refer to management of severe AEs	Permanently discontinue spartalizumab
Encephalitis (any grade)	Rule out infectious or other causes of moderate to severe neurologic deterioration, and consult with specialist.	Permanently discontinue spartalizumab
	If other etiologies are ruled out, administer corticosteroids at a dose of 1 to 2 mg/kg/day prednisone equivalents.	
Myocarditis or cardiac event grade>=3	Initiate systemic corticosteroids (prednisone or equivalent) at a dose of 1-2 mg/kg QD, and consult with specialist.	Permanently discontinue spartalizumab

Table 8-7 Mandatory dose modification requirements and recommended clinical management guidelines for infusion reaction events and cytokine release syndrome

Infusion reaction (NCI-CTCAE	E v4.03)	
Grade	Recommended Adverse Event management guidelines	Mandatory Dose Modification requirements
Grade 1 Mild reaction; infusion interruption not indicated; intervention not indicated	Increase monitoring of vital signs as medically indicated until the patient is deemed medically stable in the opinion of the investigator.	Continue spartalizumab
Grade 2 Requires infusion interruption but responds promptly to symptomatic treatment (e.g., antihistamines, NSAIDS,	 Stop Infusion Additional appropriate medical therapy may include but is not limited to: IV fluids 	spartalizumab may continue with close monitoring and premedication as per local institutional guidelines for prophylaxis of infusion reaction

Protocol Study No: Winship4463-18 Product: Siltuximab plus Spartalizumab Protocol/Version No.: 5, Date December 15, 2022

Grade	Recommended Adverse Event management guidelines	Mandatory Dose Modification requirements				
narcotics, IV fluids); prophylactic medications indicated for < =24 hrs	 Antihistamines NSAIDS Acetaminophen Narcotics Increase monitoring of vital 					
	signs as medically indicated until the patient is deemed medically stable in the opinion of the investigator.					
	If symptoms resolve within one hour of stopping drug infusion, the infusion may be restarted at 50% of the original infusion rate (e.g. from 100 mL/hr to 50 mL/hr). Otherwise dosing will be held until symptoms resolve and the patient should be re-premedicated for the next scheduled dose.					
	 Patient may be premedicated 1.5hr (± 30 minutes) prior to infusion of spartalizumab with: Diphenhydramine 50 mg po (or equivalent dose of antihistamine). 					
	 Acetaminophen 500- 1000 mg po (or equivalent dose of analgesic). 					
	 Consider discontinuation of spartalizumab in case of recurring infusion reaction despite premedication and prolonged infusion 					
Grade 3: Prolonged (i.e., not rapidly responsive to symptomatic medication and/or brief interruption of infusion); recurrence of symptoms following initial improvement; hospitalization indicated for	 Stop Infusion Additional appropriate medical therapy may include but is not limited to: IV fluids Antihistamines NSAIDS 	Permanently discontinue spartalizumab				

Protocol/Version No.: 5, Date December 15, 2022

Infusion reaction (NCI-CTCAE	E v4.03)	
Grade	Recommended Adverse Event management guidelines	Mandatory Dose Modification requirements
other clinical sequelae (e.g., renal impairment, pulmonary infiltrates) Grade 4: Life-threatening; pressor or ventilatory support indicated	 Acetaminophen Narcotics Oxygen Pressors Corticosteroids Epinephrine Increase monitoring of vital signs as medically indicated until the patient is deemed medically stable in the opinion of the investigator. Hospitalization may be indicated. 	

2nd occurrence of grade 2 irAE (including colitis/diarrhea, LFT abnormalities, rash, nephritis and other AEs as listed in table 8-6) or for grade 2 irAE lasting more than 12 weeks. Permanently discontinue spartalizumab.

6.3.2.1.2 Guidance for corticosteroids tapering for management of immune-related AEs:

Steroids should be tapered slowly and based on response/recovery of clinical symptoms. Consider to complete tapering over a period of at least 4 weeks. Slower tapering of corticosteroids therapy may be recommended if the adverse event is not showing improvement.

Protocol/Version No.: 5, Date December 15, 2022

Once corticosteroid tapering is achieved at a level of 10 mg of prednisone/day (or equivalent), spartalizumab can be restarted as indicated in the dose modification tables.

6.3.2.2 Dose modification requirements for adverse events suspected to be related to study treatment

The required dose modification and management of adverse events that are considered to be related to study medication and do not have specific management requirements noted elsewhere in the protocol are provided in Table 8-8 & Table 8-9.

Table 8-8 Mandatory dose modification requirements and recommended clinical management guidelines for hematologic adverse events suspected to study treatment

Hematologic su	spected AEs (NCI-CTCAE v4.03)	
Grade	Recommended Adverse Event management guidelines	Mandatory Dose Modification requirements
Neutropenia		
Grades 1, 2	NA	Continue spartalizumab and siltuximab
Grade 3, 4	Monitoring blood test more frequently (every 7 days for grade 3, and 3-5 days for grade 4) Consider consulting with a specialist, initiation of corticosteroids or other therapies as medically appropriate and as per institutional guidelines.	1st occurrence: Interrupt spartalizumab and siltuximab until toxicity recovers to Grade ≤2 or baseline. Once recovered restart spartalizumab and siltuximab treatment at the same dose and schedule Grade 4 febrile neutropenia or thrombocytopenia should lead to permanent discontinuation of spartalizumab and siltuximab 2nd occurrence: Interrupt spartalizumab and siltuximab until toxicity recovers to Grade ≤2 or baseline Once recovered restart spartalizumab and siltuximab treatment at the same dose and schedule
		AE resolution to ≤ Grade 2 or baseline must occur within a maximum period of 12 weeks since Grade 3 or 4 event has been identified, otherwise spartalizumab

Grade	Recommended Adverse Event management guidelines	Mandatory Dose Modification requirements
		and siltuximab must be permanently discontinued
		3 rd occurrence:
		Permanently discontinue spartalizumab and siltuximab
Febrile Neutropenia	Apply Institutional guidelines	Follow- neutropenia Grade 4 requirements (above)
Thrombocytopeni	ia (NCI-CTCAE v4.03)	
Grade 1, 2, 3 without clinical significant bleeding	Grade 3: monitoring blood test more frequently (every 7 days)	Continue spartalizumab and siltuximab
Grade 3 with	Monitoring blood test more frequently	1 st occurrence:
clinical significant bleeding OR Grade 4	(every 3-5 days) Consider consulting with a specialist, initiation of corticosteroids or other therapies as medically appropriate and as per institutional guidelines.	 Interrupt spartalizumab and siltuximab until toxicity resolves to Grade ≤2 or baseline. Once recovered restart spartalizumab and siltuximab at the same dose and schedule
		2 nd occurrence:
		 Interrupt spartalizumab and siltuximab until toxicity resolves to Grade ≤2 or baseline Once recovered restart spartalizumab and siltuximab at the same dose and schedule
		AE resolution to ≤ Grade 2 or baseline must occur within a maximum period of 12 weeks since Grade 3 with clinically significant bleeding or Grade 4 event has been identified, otherwise spartalizumab and siltuximab must be permanently discontinued.
		3 rd occurrence:
		permanently discontinue spartalizumab and siltuximab

Protocol/Version No.: 5, Date December 15, 2022

Table 8-9 Mandatory dose modification requirements and recommended clinical management guidelines for non-hematologic adverse events suspected related to study treatment (excluding alopecia, grade 2 fatigue and irAE)

Grade	Recommended Adverse Event management guidelines	Mandatory Dose Modification requirements					
Grade 1-2 tolerable	Monitor closely	Continue spartalizumab and siltuximab treatment at the					
	 Provide supportive care according to institutional standards 	same dose and schedule					
Grade 2 intolerable or	 Monitor closely 	1 st or 2 nd occurrence:					
Grade 3	 Provide supportive care according to institutional standards 	 Interrupt spartalizumab and siltuximab until toxicity recovers to Grade ≤1 or 					
	 Consider consulting with a specialist, initiation of corticosteroids or other therapies as medically appropriate and as per institutional guidelines. 	 baseline. Once recovered restart spartalizumab and siltuximab at the same dose and schedule 					
		AE resolution to Grade ≤1 or baseline must occur within a maximum period of 12 weeks since intolerable Grade 2 or Grade 3 event has been identified, otherwise spartalizumab and siltuximab must be permanently discontinued.					
		3 rd occurrence: Permanently discontinue spartalizumab and siltuximab					
Grade 4	Monitor closely	1 st occurrence:					
	 Provide supportive care according to institutional standards Consider consulting with a specialist, initiation of corticosteroids or other therapies as medically appropriate and as per institutional guidelines. 	 Interrupt spartalizumab and siltuximab Consider permanently discontinuing spartalizumab. If benefit risk assessment support treatment continuation, restart spartalizumab and siltuximab at the same dose and schedule. 					

Protocol/Version No.: 5, Date December 15, 2022

Non-Hematologic suspected AEs (except Grade 2 alopecia, Grade 2 fatigue, irAE) (NCI-CTCAE v4.03)						
Grade	Recommended Adverse Event management guidelines	Mandatory Dose Modification requirements				
		2 nd occurrence:				
		Permanently discontinue spartalizumab and siltuximab				

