6.3.1 Dose modification and dose interruption

For patients who do not tolerate the protocol-specified dosing schedule, dose interruptions are mandated in order to allow the patient to continue the study treatment. Dose interruption for spartalizumab and/or siltuximab includes delaying or withholding the treatment for any reason as well as an interruption of treatment during an infusion.

The following sections addresses the specific instructions for mandatory dose modifications and recommended management for adverse events considered suspected to be related to spartalizumab and/or siltuximab. These modifications/interruptions must be recorded on the Dosage Administration Record CRF.

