The dosing modification requirements are mandatory, however, the AE management guidelines are recommendations and can be modified according to the local practices.

Table 8.0 Mandatory dose modification requirements and recommended clinical management guidelines for potential immune-related diarrhea/colitis

Diarrhea/Colitis (NCI-CTCAE v	1100/	
Grade	Recommended Adverse Event management guidelines	Mandatory Dose Modification requirements
Grade 1 (< 4 bowel actions per day over baseline) mild Grade 2 (4-6 bowel actions per day over baseline) and / or abdominal pain/ blood in stool.	 Diet Hydration Loperamide: initially 4 mg, followed by 2 mg every four hours or after every unformed stool; maximum 16 mg/day. Continue until diarrhea free for 12 hours; Diarrhea > 24h: loperamide 2 mg every two hours; maximum 16 mg/day. Consider adding oral antibiotics. Diarrhea > 48hrs: loperamide 2 mg every two hours; maximum 16 mg/day. Consider other second-line therapies for diarrhea (e.g: (octreotide, oral diphenoxylate) and oral antibiotics If Grade 2 and no improvement in 5 days may require oral steroids If Grade 2 diarrhea persists >1 week consider Gl consultation and endoscopy to 	Continue spartalizumab treatment If diarrhea is Grade 2, despite loperamide at 2 mg every two hours for > 48hrs:

Protocol/Version No.: 5, Date December 15, 2022

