Grade 3 or 4: AST or ALT >5.0xULN and/or bilirubin > 3.0x ULN	 Monitor hepatic laboratory tests more frequently (every 2-3 days) until returned to baseline values. Consider viral serology (i.e. hepatitis A/B/C, CMV, and rule out other potential cause of liver injury such as conmeds or alcohol), consultation with hepatologist and liver biopsy to establish etiology of hepatic injury If after 2-3 days new liver assessment shows worsening of laboratory test consider to initiate treatment with steroids prednisone 1-2 mg/kg/day or IV equivalents. Add prophylactic antibiotics for opportunistic infections as appropriate When symptoms/liver function tests improve to Grade ≤1, taper steroids over at least 4 weeks. If serum transaminase levels or bilirubin do not decrease 48 hours after initiation of systemic steroids, oral mycophenolate mofetil 500 mg every 12 hours may be given as per local treatment guidance. Infliximab is not recommended due to its potential for hepatotoxicity 	 Permanently discontinue spartalizumab Patients with baseline grade 2 AST/ALT value (>3.0-5.0 ULN) will discontinue spartalizumab treatment if value increased to grade 3 with increase >=2x baseline

Table 8-2 Mandatory dose modification requirements and recommended clinical management guidelines for potential immune-related skin events

Rash Events (NCI-CTCAE v4.03)		
Grade	Recommended Adverse Event management guidelines	Mandatory Dose Modification requirements
Grade 1: Rash covering < 10% Body Surface Area (BSA)	 Initiate prophylactic and symptomatic treatment measures. Consider use of topical corticosteroids or urea containing creams in combination with oral antipruritics or moderate strength topical steroid (hydrocortisone 2.5% cream or fluticasone propionate 0.5% cream) 	Continue spartalizumab treatment
Grade 2: 10-30% of BSA	 Reassess after 2 weeks. If tolerable, treat as per Grade 1; If intolerable, initiate systemic steroids (e.g. oral prednisolone 0.5-1mg/kg daily) and consider dose interruption until tolerable or recovery to grade <=1 or baseline; once recovered resume spartalizumab treatment at the same dose and schedule. If symptoms persist or recur consider skin biopsy. 	Continue spartalizumab treatment AE resolution to ≤1 or baseline must occur within a period of 12 weeks since Grade 2 event has been identified, otherwise spartalizumab must be permanently discontinued.

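### Table 8-2's mandatory cell for Grade 2 rash continues spartalizumab with no exception for an intolerable rash, which fits neither the cell beside it nor sections 6.3.1 and 6.4.2

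*Combined protocol and SAP*

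**What the plan says.** The Grade 2 rash row of Table 8-2 (protocol section 6.3.2.1.1) has two cells.

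- **Recommended management.** A tolerable rash is handled as Grade 1. Otherwise: "If intolerable, initiate systemic steroids (e.g. oral prednisolone 0.5-1mg/kg daily) and consider dose interruption until tolerable". Recovery to Grade 1 or baseline is given as an alternative end to the interruption, and then: "once recovered resume spartalizumab treatment at the same dose and schedule".
- **Mandatory dose modification.** "Continue spartalizumab treatment AE resolution to ≤1 or baseline must occur within a period of 12 weeks since Grade 2 event has been identified". If that limit is missed, spartalizumab stops permanently. The cell does not separate tolerable from intolerable rash.

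The text that introduces these tables ranks the two columns: "The dosing modification requirements are mandatory, however, the AE management guidelines are recommendations and can be modified according to the local practices".

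Three other places bear on the same patient:

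- Section 6.3.1: "For patients who do not tolerate the protocol-specified dosing schedule, dose interruptions are mandated".
- Section 6.4.2 requires steroids used for immune-related events to be tapered below 10 mg/day prednisone equivalent before the next study dose, and lets that dose be delayed by up to 12 weeks.
- Section 6.3.2.1.2 allows spartalizumab to restart once the taper has reached 10 mg/day.

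**The concern.** The only dosing action the row offers for an intolerable rash, a possible interruption followed by resumption, sits in the column that does not bind. The column that binds says to continue. An investigator who starts the advised steroid and then looks up the dosing rule finds an instruction that other parts of the protocol do not let them carry out.

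Two things are at stake. The first is a clear instruction for the patient on the day the next infusion is due. The second is the dose-modification summary in section 12.5.1.3, which counts skipped and delayed doses and the main reasons for them. If investigators resolve the conflict differently, similar rashes enter that summary differently.

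**Working it through.** The plan states no figure on this point, so the check sets the texts side by side and adds simple arithmetic.

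**1. The two cells.** For a tolerable Grade 2 rash they agree: treat and continue. For an intolerable one, the recommended cell allows a hold and describes a restart, while the mandatory cell contains neither. For Grade 2 liver, renal and lung events (Tables 8-1, 8-3 and 8-4), the interruption is written in the mandatory column.

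**2. The mandatory cell against the steroid limit in 6.4.2.** Daily dose = mg/kg × body weight. The weights are assumptions.

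| Weight | 0.5 mg/kg | 1 mg/kg |
|---|---|---|
| 40 kg | 20 mg | 40 mg |
| 60 kg | 30 mg | 60 mg |
| 80 kg | 40 mg | 80 mg |

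The advised dose is below 10 mg/day only under 10 / 0.5 = 20 kg, or under 10 / 1 = 10 kg at the upper dose. An adult still taking it cannot receive the next infusion under 6.4.2, although the mandatory cell says to continue.

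**3. Whether the conflict reaches an infusion.** Section 6.3.2.1.2 suggests tapering over at least 4 weeks (28 days). Cycles are 3 weeks with a 3-day window, so the next infusion falls at most 21 + 3 = 24 days after the last one. A taper begun after one on-schedule infusion would still be running at the next. Whether it is already below 10 mg/day by then depends on how it is stepped down. The conflict can therefore readily arise, but not in every case.

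**4. The mandatory cell against 6.3.1.** If an intolerable rash counts as not tolerating the dosing schedule, 6.3.1 mandates interruption where Table 8-2 mandates continuation.

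**5. The restart threshold.** Section 6.3.2.1.2 permits restart at 10 mg/day; section 6.4.2 requires less than 10 mg/day. At exactly 10 mg/day they give different answers.

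**6. Attribution.** Table 8-9 interrupts both drugs for events in its row "Grade 2 intolerable or" Grade 3, but its title excludes immune-related events. Section 6.3.2 lists rash as a siltuximab effect. The numbered siltuximab rules in 6.3.3 have no rash item and refer the reader to 6.3.2.2, where Table 8-9 sits. The same rash can thus fall under either table, and nothing says how an unclear case is assigned.

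**7. Frequency.** Table 3 (section 4.1.2.1) gives rash of any grade as 15/53 = 28.3% with siltuximab and Grade 3-4 rash as 1/53 = 1.9%. It gives no Grade 2 rate. For an assumed rate p of intolerable Grade 2 rash, the chance of at least one case among N treated patients is 1 − (1 − p)^N:

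| p (assumed) | N = 27 | N = 42 |
|---|---|---|
| 1% | 24% | 34% |
| 2% | 42% | 57% |
| 5% | 75% | 88% |
| 10% | 94% | 99% |

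**The case against.** The strongest reply is that the protocol already settles the matter. The recommended cell only asks the investigator to consider interruption, and the ranking of the columns says which one governs. Section 6.2 lets spartalizumab be interrupted for up to 12 weeks, and 6.4.2 would hold any patient still on 0.5-1 mg/kg whichever cell is read.

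Much of this stands, and it limits what can be claimed:

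- A reader might infer that the two cells give opposite orders. They do not: one is a discretionary option, the other a requirement.
- A reader might infer that any interruption would be a protocol deviation. That is not established, because 6.2, 6.3.1 and 6.4.2 each permit or require a hold.
- A reader might take Table 8-9 as a direct contradiction. Its scope excludes immune-related events, so it shows a difference by attribution. Section 6.3.2 allows independent modification where an event is clearly attributed to one drug.

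The reply does not rescue the mandatory cell. If 6.4.2 holds the patient regardless, then the cell labelled mandatory is the one that cannot be followed as written. Ranking the columns of Table 8-2 does not rank that table against 6.3.1 or 6.4.2.

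**Conclusion.** The inconsistency is real and narrow. The mandatory Grade 2 rash cell has no exception for an intolerable rash. It omits the interruption allowed beside it and does not fit 6.4.2 for an adult still on the advised steroid dose (20-80 mg/day at an assumed 40-80 kg, against a limit of below 10 mg/day). The conflict with 6.3.1 rests on reading an intolerable rash as intolerance of the dosing schedule.

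Two larger conclusions are tempting but unsupported. The 28% in Table 3 might suggest that this event is likely, but it is rash of any grade, over the first eight infusions, in patients with Castleman's disease; the table of assumed rates shows only how the chance varies. A reader might also infer that the conflict distorts dose escalation. Section 6.2.2 requires two infusions of both drugs and at least 6 weeks of safety assessment, or a DLT within the first 6 weeks. It does not say that a late second infusion makes a patient non-evaluable, and 6.7.1 allows a further patient to be enrolled when one is. An effect is possible but not shown.

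What remains is an unclear dosing instruction that bears on patient safety, and uneven recording of dose delays under 12.5.1.3.

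**What to change.** The clinical team should:

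- reconcile the two Grade 2 cells of Table 8-2 with each other and with 6.3.1, 6.3.2.1.2 and 6.4.2;
- settle the restart threshold, which is 10 mg/day in 6.3.2.1.2 and below 10 mg/day in 6.4.2;
- state how a rash of unclear attribution is assigned between Table 8-2 and Table 8-9.

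Which rule should stand is a clinical decision, and none is proposed here. The cost is a short text amendment across these sections, with its usual approval. It needs no change to the sample size, visit schedule or analyses.

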6.1.4 Screen Failures

Minimal data for subjects who fail screening will be collected such as demographic information and the reason for screen failure. Such subjects may be re-screened at the discretion of the investigator after approval by the Data and Safety Monitoring Committee (DSMC). The reason for the need to re-screen a subject will be documented in the subject's source documents.

Trial Treatments 6.2

The treatment to be used in this trial is outlined below in Table

Drug	Dose/Potency	Dose	Route of	Regimen/Treatment Period
		Frequency	Administration	
Spartalizumab	300 mg	Q3W	IV infusion	Day 1 of each 3 week cycle
Siltuximab	As Below	Q 3W	IV Infusion	Day 1 of each 3 week cycle

Table 5. Trial Treatment

Siltuximab will be infused first. Patients will be observed for at least 1 hour post infusion of siltuximab.

Spartalizumab will be administered via intravenous infusion over 30 minutes (up to 2 hours, if clinically indicated) once every 3 weeks. The dose may be interrupted for up to 12 weeks. The safety assessments should be performed according to the actual day of infusion.

Protocol/Version No.: 5, Date December 15, 2022

Patients should be closely observed for potential infusion-related reactions including rigors, chills, wheezing, pruritus, flushing, rash, hypotension, hypoxemia, and fever, and vital signs monitored more frequently if clinically indicated, during and for at least 4 hours after the first two spartalizumab infusions. The same may apply for the subsequent spartalizumab infusions if medically indicated. Patients should be further provided instructions to notify study personnel if symptoms of infusion reaction occur after any spartalizumab infusion.

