Symptomatic endocrinopathy (e.g., hypophysitis, adrenal insufficiency, hypothyroidism, hyperthyroidism)	 Consider Endocrinology consultation Rule out infection/sepsis and other alternative causes with appropriate cultures and imaging Treat with an initial dose of methylprednisolone 1 to 2 mg/kg intravenously followed by oral prednisone 1 to 2 mg/kg per day. (only for lifethreatening endocrinopathies) Replacement of appropriate hormones may be required as the steroid dose is tapered Hypophysitis with clinically significant adrenal insufficiency and hypotension, dehydration, and electrolyte abnormalities (such as hyponatremia and hyperkalemia) constitutes adrenal crisis Consider hospitalization and intravenous methylprednisolone should be initiated. 	Interrupt spartalizumab until recovery to mild or no symptoms, and controlled with hormone replacement therapy Once recovered or controlled with hormone replacement, restart spartalizumab at the same dose and schedule Hypothyroidism may be managed with replacement therapy without treatment interruption (unless lifethreatening) Permanently discontinue spartalizumab for lifethreatening endocrinopathies (i.e. hyperthyroidism, adrenal insufficiency, hypophysitis) or recurring severe/lifethreatening events not controlled by hormone replacement therapy.
Autoimmune diabetes (Grade 3 or symptomatic hyperglycemia)	Initiated: Initiate anti-glycemic therapy (i.e. insulin) as medically indicated and monitor glucose levels regularly until metabolic control is achieved	Interrupt spartalizumab until recovery to grade 1 or baseline Once recovered, restart spartalizumab treatment at the same dose and schedule
Autoimmune diabetes (Grade 4 hyperglycemia or life- threatening complications)	Same as Grade 3	 Second occurrence: permanently discontinue Permanently discontinue spartalizumab

Management for immune-related:

Protocol/Version No.: 5, Date December 15, 2022

a. For non-life-threatening immune-related endocrinopathy, the administration of corticosteroids can be omitted, and the patient can be treated with physiologic replacement of the deficient hormone (e.g. provide levothyroxine for immune-related hypothyroidism, and omit administration of corticosteroids).

b. Use corticosteroids only used if endocrinopathy is life-threatening or as physiologic replacement for primary or secondary adrenal insufficiency.

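### Table 8-5, symptomatic endocrinopathy: the hold on spartalizumab ends on two joint conditions but the restart needs only one, so a patient recovered without hormone replacement is both held and restarted

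*Combined protocol and SAP*

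**What the plan says.** Table 8-5 sits in Section 6.3.2.1.1 and covers immune-related endocrine events. The row at issue is labelled "Symptomatic endocrinopathy (e.g., hypophysitis, adrenal insufficiency, hypothyroidism, hyperthyroidism". Its dose-modification cell contains, in sequence:

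- the hold: "Interrupt spartalizumab until recovery to mild or no symptoms, and controlled with hormone replacement therapy";
- the restart: "Once recovered or controlled with hormone replacement, restart spartalizumab at the same dose and schedule";
- an exemption: "Hypothyroidism may be managed with replacement therapy without treatment interruption (unless lifethreatening";
- a rule for permanent discontinuation of life-threatening events, and of recurring severe events that replacement does not control.

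The management column of the same row makes hormone replacement conditional: "Replacement of appropriate hormones may be required as the steroid dose is tapered".

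The text introducing the tables fixes their status: "The dosing modification requirements are mandatory, however, the AE management guidelines are recommendations and can be modified according to the local practices". The hold and restart sentences are in the binding column.

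**The concern.** One decision, when to resume spartalizumab, is stated twice in one cell with different logic. The hold lasts until symptoms are mild or absent *and* replacement controls the event. The restart is triggered by recovery *or* control by replacement. A site following the first sentence and a site following the second would treat the same patient differently, and each could cite mandatory text.

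The event is foreseeable. Section 5.4 lists endocrine toxicities, hyperthyroidism among them, with the typically most frequent immune-mediated events. Section 9.1.3 makes them events of special interest. Section 6.3.2.1.1 expects most immune-related events within weeks to three months of starting treatment.

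At stake is consistent dosing across patients. During escalation it could also affect the timing of the second spartalizumab infusion, because Section 6.2.2 counts a patient without a DLT as evaluable only after at least two infusions of both drugs and six weeks of safety assessment.

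**Working it through.** The plan attaches no figure to this rule, so there is none to reproduce. The check is logical.

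**Step 1: the two conditions.** Let A be symptoms recovered to mild or none, and B be the event controlled by hormone replacement.

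- End of hold (first sentence): A and B.
- Restart (second sentence): A or B.

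| A met | B met | Hold over? | Restart triggered? | Sentences agree? |
|---|---|---|---|---|
| yes | yes | yes | yes | yes |
| no | no | no | no | yes |
| yes | no | no | yes | **no** |
| no | yes | no | yes | **no** |

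They disagree in 2 of 4 states, namely whenever exactly one condition holds.

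**Step 2: can those states occur?**

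- *A without B.* Yes. The row names hyperthyroidism, an excess of hormone, while note a under Table 8-5 describes replacement as supplying a deficient one. The management column also makes replacement conditional. A patient who recovers without it satisfies A and not B: still held by the first sentence, restarted by the second.
- *B without A.* Doubtful. The restart requires control by replacement, not merely being on it. A patient with more than mild symptoms would rarely be called controlled, so this state may be nearly empty.

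**Step 3: which patients remain.** Asymptomatic events continue treatment under their own row. Hypothyroidism on replacement may avoid interruption unless life-threatening. Life-threatening events go to permanent discontinuation. What remains is chiefly non-life-threatening symptomatic hyperthyroidism, hypophysitis and adrenal insufficiency, and within these only patients who meet exactly one condition.

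**Step 4: does other text settle it?**

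- Section 6.3.2.1.2, on steroid tapering, says "spartalizumab can be restarted as indicated in the dose modification tables", which leads back to this cell.
- The general list in Section 6.3.2 governs permanent discontinuation, not restart.
- Neighbouring cells keep one condition. In the nephritis cells (Table 8-3) and the Grade 3 autoimmune diabetes row (Table 8-5), the restart simply refers to the recovery already defined. Only the symptomatic endocrinopathy cell adds an alternative trigger.

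**Step 5: effect in the DLT window.** Cycles last 3 weeks, so the second infusion is due at about 3 weeks. The first on-treatment thyroid panel in the flow chart is also at cycle 2. The window is 6 weeks, which leaves 6 − 3 = 3 weeks in which a delayed second infusion would still fall inside it. Siltuximab continues during a temporary hold (Section 6.3.2), so only the spartalizumab count would lag. Section 6.7.1 allows a new enrolment to be considered if too few patients in the cohort are evaluable.

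**The case against.** The best defence is that *recovered* in the second sentence is shorthand for the whole hold condition. The restart then becomes (A and B) or B, which reduces to B. If control by replacement also implies mild symptoms, the hold reduces to B as well and the sentences agree. That removes the contradiction only by leaving a recovered patient who never needed replacement with no route back to treatment. A looser defence is that the first sentence means control by replacement where replacement is used. That is plausible, but the cell does not say it. Section 6.3.2.1.1 encourages investigators to contact the sponsor about cases outside the instructions, which would soften the problem case by case without giving one rule.

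The defence is right about how far the harm extends. A reader might infer three stronger things:

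- *That still-symptomatic patients would be re-dosed.* The restart wording requires control, so this is largely unsupported.
- *That a recovered hyperthyroid patient would lose spartalizumab at 12 weeks, and then usually siltuximab.* Section 6.2 says "The dose may be interrupted for up to 12 weeks" but states no consequence. The persistent-event rule for spartalizumab in Section 6.3.2 applies to reactions that have not recovered and excludes endocrinopathies controlled by replacement. The explicit trigger for interruption beyond 12 weeks is in the siltuximab list. The endocrinopathy cell has no 12-week clause. Section 6.3.2 also allows single-agent continuation for patients with objective benefit.
- *That a number of patients can be stated.* The documents give no endocrinopathy rate. Assuming 5% to 15% of the 27 to 42 treated patients gives 0.05 × 27 = 1.35 to 0.15 × 42 = 6.3 entering the row. That is an upper bound on an assumed rate, since it removes neither exempt hypothyroidism nor patients who meet both conditions or neither.

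**Conclusion.** The contradiction is real and sits in binding text. The hold and restart sentences disagree whenever exactly one condition is met, and nothing else in the documents resolves it. In practice it concerns a patient whose symptomatic event has resolved without hormone replacement, most plainly the hyperthyroidism the row names.

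The size is modest. Sites may dose the same event inconsistently, and an escalation patient's second infusion could be late. The 3-week margin and the option to enrol a new patient make a changed escalation decision unlikely. No sample size, endpoint or planned analysis changes. The conclusion rests on reading *and* and *or* in their ordinary sense and on hyperthyroidism not being treated by replacing hormone. It takes no view on which restart condition is clinically right.

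**What to change.** At the next amendment the sponsor's clinical team should reconcile the two sentences so that the condition ending the hold and the condition for restart are identical. The cell should also make clear how that condition applies to listed events not treated with hormone replacement. The choice of condition is theirs. The hypothyroidism exemption and the life-threatening rule can stay as separate statements, so that the scope of the reworded rule is plain.

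The cost is one reworded table cell and a note to sites, with no statistical cost. If any patient has already been managed under this cell, a short record of which sentence was followed would let dose delays in the Section 12.5.1.3 summary be read correctly.
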